### **1. Background and Rationale**

Gestational diabetes mellitus (GDM) is a common metabolic disorder of pregnancy and is associated with significant short- and long-term risks for both mother and child. In Vietnam, the prevalence of GDM has increased substantially in recent years, while systematic screening, counselling uptake, and long-term self-management support remain limited. Although pharmacological treatment is available for severe cases, most women rely heavily on lifestyle modification, informal family support, and self-care practices for disease management.

Previous international studies indicate that self-care and social support interventions may improve quality of life, self-efficacy, and selected maternal and neonatal outcomes among women with GDM. However, such interventions are highly context-dependent, shaped by social norms, family structures, and health system capacity. To date, no structured self-care or informal support intervention for GDM has been developed or evaluated in the Vietnamese context.

The VALID-II study was therefore designed as a feasibility intervention study, with the primary purpose of determining whether a co-created self-care and informal support intervention can be implemented, accepted, and retained among women with GDM in northern Vietnam. The study is intentionally positioned as a preparatory step prior to a future randomized controlled trial and is embedded

within a larger observational cohort to allow simultaneous collection of maternal and neonatal outcome data .

## 2. Study Objectives

The primary objective of VALID-II is to evaluate the feasibility of a co-created self-care and informal support intervention for women diagnosed with GDM. Feasibility is defined as the extent to which the intervention can be successfully delivered and maintained under real-world conditions and is assessed through recruitment, retention, and acceptability.

Secondary objectives are exploratory and aim to assess the potential effects of the intervention on selected maternal and neonatal health outcomes, including self-care agency, perceived social support, breastfeeding practices, pregnancy outcomes, and neonatal morbidity. These analyses are intended to generate preliminary estimates of effect size and variance to inform the design of a future definitive trial.

## 3. Study Design

VALID-II is a two-arm, non-randomised feasibility intervention study with a delayed intervention design. The study is conducted in two sequential phases rather than in parallel.

In the first phase, women diagnosed with GDM are allocated to a control group and receive standard care. During this phase, a subgroup of women and their informal support persons participate in an embedded ethnographic study. Findings from this qualitative work inform the co-creation of the intervention.

In the second phase, after a delay of approximately three months, a new group of women diagnosed with GDM is allocated to the intervention arm and receives the co-created intervention in addition to standard care. This delayed design was chosen to allow meaningful intervention development grounded in participants' lived experiences and to ensure cultural relevance.

#### 4. Study Setting

The study is conducted in Thai Binh Province, northern Vietnam. Participants are recruited from two health facilities: Thai Binh Maternity Hospital, a public hospital providing antenatal care and delivery services, and Kim Ngan Clinic, a private clinic providing antenatal care only. Both facilities serve urban and peri-urban populations and routinely perform oral glucose tolerance testing during pregnancy.

#### 5. Study Population

Pregnant women attending antenatal care at the study sites are eligible for screening. Women are eligible for inclusion if they are  $\leq 28$  weeks' gestation at enrolment, reside in Thai Binh Province, are able to read and speak Vietnamese, and provide written informed consent. Both singleton and multiple pregnancies are eligible, and a history of GDM in a prior pregnancy does not preclude participation.

Women are excluded if they have known pregestational diabetes (type 1 or type 2) or severe chronic disease that would substantially interfere with pregnancy management or study participation.

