## 6. Recruitment and Study Procedures

At the first antenatal care visit, eligible women are informed about the study by trained study nurses or midwives. After providing written informed consent, participants complete a baseline questionnaire and are scheduled for a standard 75-g oral glucose tolerance test (OGTT) at gestational age 24–28 weeks.

OGTT procedures follow WHO and IADPSG diagnostic criteria. Women diagnosed with GDM are invited to participate in follow-up data collection and allocated to either the control or intervention group depending on study phase. Women without GDM continue routine care but contribute delivery and neonatal outcome data via medical records.

Women diagnosed with GDM complete additional questionnaires during pregnancy (32–40 weeks gestation) and at 8–12 weeks postpartum. Delivery and neonatal outcomes are abstracted from medical records.

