## 8. Outcome Measures

The primary outcomes relate to feasibility:

- Recruitment is defined as the proportion of eligible women who consent to participate.
- Retention is defined as the proportion of enrolled women who complete delivery and postpartum follow-up.
- Acceptability is assessed using both quantitative Likert-scale measures and qualitative ethnographic interviews.

Secondary outcomes include maternal outcomes (e.g., self-care agency, perceived social support, gestational weight gain, HbA1c, breastfeeding practices, postpartum depression) and neonatal outcomes (e.g., birth weight, gestational age, large for gestational age, macrosomia, neonatal hypoglycaemia).

All outcomes and measurement tools are predefined and aligned with the published protocol .

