## 9.2 Analysis of Feasibility Outcomes

Recruitment will be calculated as the proportion of eligible women diagnosed with GDM who consent to participate in the study. Retention will be calculated as the proportion of enrolled women who provide delivery data and complete the postpartum questionnaire. Both outcomes will be presented as percentages with corresponding 95% confidence intervals.

Acceptability will be analysed using a mixed-methods approach. Quantitative acceptability scores will be summarised using means, standard deviations, medians, and ranges. The predefined progression criterion is a mean Likert score greater than 3. Qualitative data from ethnographic interviews will be analysed thematically to explore participants' experiences, perceived usefulness, and barriers to engagement with the intervention.

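### The primary recruitment outcome, as written, does not capture women who refuse: its denominator differs between sections and, in the SAP, is formed after consent

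*Combined protocol and SAP*

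**What the plan says.** Five statements bear on the recruitment outcome.

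- Section 5 includes consent in the list of conditions a woman must meet to be eligible for inclusion: "are able to read and speak Vietnamese, and provide written informed consent".
- Section 6 uses the same word for women who have not yet been asked: "eligible women are informed about the study by trained study nurses or midwives". Consent comes next, and the diagnostic test after that: "After providing written informed consent, participants complete a baseline questionnaire and are scheduled for a standard 75-g oral glucose tolerance test (OGTT".
- Section 6 then adds a second step after diagnosis: "Women diagnosed with GDM are invited to participate in follow-up data collection and allocated to either the control or intervention group depending on study phase".
- Section 8 defines the primary outcome over all eligible women: "Recruitment is defined as the proportion of eligible women who consent to participate".
- Section 9.2 defines it over a narrower group: "Recruitment will be calculated as the proportion of eligible women diagnosed with GDM who consent to participate in the study". On reporting, it says: "Both outcomes will be presented as percentages with corresponding 95% confidence intervals".

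The only progression criterion stated concerns acceptability: "The predefined progression criterion is a mean Likert score greater than 3". The documents give no sample size, expected consent rate or recruitment threshold. They also describe no log of women who were approached, declined or were missed.

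**The concern.** A recruitment proportion is useful only if women who say no stay in the denominator. Here they can be lost in two ways. The first is verbal: if consent is part of eligibility, a woman who declines is not eligible and is removed. The second lies in the order of procedures: if the denominator is women with a GDM diagnosis, and the study makes that diagnosis only after consent, those who declined at the first visit are never in it.

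Recruitment is one of three primary feasibility outcomes, and the study is presented as preparation for a randomised trial. If the reported figure omits first-visit refusals, it can look high and precise while saying nothing about how many women agree when first asked. Two analysts following sections 8 and 9.2 could also report different numbers from the same data.

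**Working it through.** The plan states no recruitment figure to reproduce, so the check compares the readings of the definition.

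**Notation**

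- E: women at the first visit who meet the gestation, residence and language criteria and have no exclusion.
- C: those of E who give written consent at that visit.
- G: those of C diagnosed with GDM at the study OGTT.
- F: those of G who accept the post-diagnosis invitation.

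By the sequence in section 6, F is contained in G, G in C, and C in E.

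**Four readings**

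1. Section 8 with section 5 taken literally: eligible women are C, so the ratio is C/C = 100% for any C above zero.
2. Section 8 with *eligible* in section 6's pre-consent sense: C/E, the real first-visit consent rate.
3. Section 9.2 counting first-visit consent: every woman in G has already consented, so the ratio is G/G = 100%.
4. Section 9.2 counting the post-diagnosis invitation: F/G, acceptance of follow-up among women who had already consented.

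Readings 3 and 4 take the denominator to be women diagnosed through the study OGTT.

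**Illustration.** All inputs are assumptions: E = 1,000, GDM in 20% of tested women, first-visit consent c1 of 50%, 70% or 90%, follow-up acceptance c2 of 80% or 95%. Then G = 1,000 × c1 × 0.20 and F = G × c2.

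| c1 | c2 | G | F | Reading 1 | Reading 2 (C/E) | Reading 3 (G/G) | Reading 4 (F/G) |
|---|---|---|---|---|---|---|---|
| 50% | 80% | 100 | 80 | 100% | 50% | 100% | 80% |
| 50% | 95% | 100 | 95 | 100% | 50% | 100% | 95% |
| 70% | 80% | 140 | 112 | 100% | 70% | 100% | 80% |
| 70% | 95% | 140 | 133 | 100% | 70% | 100% | 95% |
| 90% | 80% | 180 | 144 | 100% | 90% | 100% | 80% |
| 90% | 95% | 180 | 171 | 100% | 90% | 100% | 95% |

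Readings 3 and 4 do not move with c1. The GDM frequency cancels, so the 20% does not affect any ratio.

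**Confidence intervals**

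- For a result of n/n, the exact (Clopper-Pearson) lower 95% limit is 0.025^(1/n): 92.9% at n = 50, 96.4% at n = 100 and 98.2% at n = 200 (n assumed). On readings 1 and 3 the interval would look tight whatever the true uptake.
- For reading 2 with an assumed 100 eligible women, the Wilson interval [p + z²/2n ± z√(p(1−p)/n + z²/4n²)] / (1 + z²/n) with z = 1.96 gives 50% (40.4 to 59.6), 70% (60.4 to 78.1) and 90% (82.6 to 94.5).

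**The case against.** The strongest reply is that listing consent among inclusion conditions is ordinary drafting. Section 6 shows what the authors meant: women are called eligible, then informed, then asked to consent. Section 8 makes sense only on that reading, and on it the proportion is measurable. Section 6 also gives women with GDM a later invitation that they can decline, so even section 9.2 can return less than 100%.

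This stands against a conclusion that a reader might infer from section 5: that recruitment is 100% by definition, whichever population is used, and so cannot be measured. The documents do not support that. It follows only from readings 1 and 3.

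The reply does not rescue section 9.2. The later invitation goes to women who had already agreed once, so it says nothing about first-visit refusals. Section 4 notes that both sites perform OGTTs routinely, so some women who declined could be diagnosed outside the study and in principle be counted, but no procedure provides for this. Nor does section 6's usage say how the number of eligible women will be obtained.

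It is also fair to say that no stated progression rule depends on recruitment, so no go/no-go decision in these documents turns on the figure. Section 8 refers to a published protocol that is not among the documents reviewed; a screening log might be described there.

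**Conclusion.** The point holds in a limited form and should be acted on. The circularity between sections 5 and 8 is a wording defect, because section 6 supplies a workable meaning of *eligible*. The substantive defect is the rule in section 9.2: with consent taken before the study OGTT, its denominator excludes first-visit refusals, and the result is either 100% or acceptance of follow-up among women already consented. Sections 8 and 9.2 also name different denominators, and neither says which consent counts.

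On size: at an assumed first-visit consent of 50% and follow-up acceptance of 80%, the same data yield 50%, 80% or 100% depending on the reading. These rates are illustrative. The conclusion about section 9.2 rests on its denominator being women diagnosed through the study OGTT, the only route to diagnosis that section 6 describes.

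A reader might go further and convert these rates into numbers of women to approach for a later trial. The documents do not allow it: that calculation also needs the GDM prevalence among women tested and the post-diagnosis acceptance rate, and neither is given.

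**What to change.** **Section 5.** Move written consent out of the eligibility list and describe it as an enrolment step. *Eligible* then means meeting the gestation, residence and language criteria with no exclusion, which matches section 6.

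**Sections 8 and 9.2.** Use the same text in both and report two recruitment proportions, each with a 95% confidence interval:

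- (a) women consenting at the first visit, divided by women eligible at that visit, and also divided by women informed at that visit;
- (b) women accepting the post-diagnosis invitation, divided by all consented women diagnosed with GDM, by phase.

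Proportion (a) keeps refusals in view. Proportion (b) keeps uptake among women with GDM, the population of the study's objective.

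**Section 6.** Add an anonymous tally at both sites: met criteria, informed, consented, declined. The difference between the first two counts shows how many eligible women were not approached.

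**Phase 1.** If no tally was kept, rebuild the denominator of (a) from the antenatal registers, or state that (a) is not estimable for that phase.

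**Cost.** Wording changes in a few sections, a tally sheet per site, possibly a register search for phase 1, and a reported figure that will probably be less favourable. The trial is ongoing, and uncounted refusals become harder to recover with time, so the tally should start first.

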## 6. Recruitment and Study Procedures

At the first antenatal care visit, eligible women are informed about the study by trained study nurses or midwives. After providing written informed consent, participants complete a baseline questionnaire and are scheduled for a standard 75-g oral glucose tolerance test (OGTT) at gestational age 24–28 weeks.

OGTT procedures follow WHO and IADPSG diagnostic criteria. Women diagnosed with GDM are invited to participate in follow-up data collection and allocated to either the control or intervention group depending on study phase. Women without GDM continue routine care but contribute delivery and neonatal outcome data via medical records.

Women diagnosed with GDM complete additional questionnaires during pregnancy (32–40 weeks gestation) and at 8–12 weeks postpartum. Delivery and neonatal outcomes are abstracted from medical records.

## 7. Intervention and Comparator

All women diagnosed with GDM receive standard care, which includes referral for counselling regarding diet, physical activity, and glucose monitoring. Because prior research indicated variable uptake of counselling, an ethical safeguard phone call is conducted by an endocrinologist to ensure that all women receive at least basic information about GDM self-care.

The intervention arm receives, in addition to standard care, a co-created self-care and informal support intervention. The intervention includes written educational materials, digital communication, peer networking, and guidance for involving family members in daily self-care practices. The precise content and delivery format are determined through an iterative co-creation process involving women with GDM, their informal support persons, and local healthcare staff.

## 8. Outcome Measures

The primary outcomes relate to feasibility:

- Recruitment is defined as the proportion of eligible women who consent to participate.
- Retention is defined as the proportion of enrolled women who complete delivery and postpartum follow-up.
- Acceptability is assessed using both quantitative Likert-scale measures and qualitative ethnographic interviews.

Secondary outcomes include maternal outcomes (e.g., self-care agency, perceived social support, gestational weight gain, HbA1c, breastfeeding practices, postpartum depression) and neonatal outcomes (e.g., birth weight, gestational age, large for gestational age, macrosomia, neonatal hypoglycaemia).

All outcomes and measurement tools are predefined and aligned with the published protocol .

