## 9.3 Analysis of Secondary Outcomes

Secondary maternal and neonatal outcomes will be analysed descriptively and exploratorily. Continuous variables (e.g., birth weight, gestational age, self-care agency scores) will be summarised using means and standard deviations or medians and interquartile ranges, depending on distribution. Binary outcomes (e.g., large for gestational age, preterm birth) will be summarised as proportions.

For exploratory comparisons between intervention and control groups, regression models will be used where appropriate. Logistic regression will be applied to binary outcomes, and linear regression to continuous outcomes. Effect estimates will be presented as odds ratios or mean differences with 95% confidence intervals. No adjustment for multiple comparisons will be performed.

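### Gestational weight gain is compared between arms without stated start and end weights or a commitment to adjust for gain before allocation at 24–28 weeks

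*Combined protocol and SAP*

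**What the plan says.** - **Outcome.** Section 8 lists gestational weight gain only as an example: "Secondary outcomes include maternal outcomes (e.g., self-care agency, perceived social support, gestational weight gain, HbA1c". The text supplies no start weight, end weight, source or timing. The same section adds: "All outcomes and measurement tools are predefined and aligned with the published protocol". That publication is not among the documents reviewed.
- **Timing and allocation.** Under section 6, participants are "scheduled for a standard 75-g oral glucose tolerance test (OGTT) at gestational age 24–28 weeks". Those found to have GDM are then "allocated to either the control or intervention group depending on study phase".
- **Design.** Section 3 describes a "two-arm, non-randomised feasibility intervention study with a delayed intervention design", with the control phase first and the intervention phase after it.
- **Model.** Section 9.3: "Logistic regression will be applied to binary outcomes, and linear regression to continuous outcomes". Results are given as mean differences with 95% confidence intervals.
- **Adjustment.** Section 9.4 adjusts only if an imbalance that matters clinically is found. Its examples are the mother's age, BMI (no time point given), parity and gestational age at diagnosis. The list is open-ended, but neither weight nor gain at diagnosis is on it.
- **Purpose.** Section 2 says the secondary analyses should "generate preliminary estimates of effect size and variance to inform the design of a future definitive trial".

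**The concern.** Weight gained before a woman enters an arm cannot be an effect of that arm. If the outcome is counted over the whole pregnancy, the arm contrast adds two parts: gain after allocation, which the intervention might change, and gain before it, which it cannot.

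Randomisation would balance the earlier part on average. Here the two arms are women from different calendar periods, so nothing in the design does so. The adjustment rule does not fill the gap, because it is conditional and does not name the relevant variable. BMI cannot be assumed to stand in for it: no time point is given, and section 5 allows enrolment up to 28 weeks.

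At stake are the two quantities that section 2 wants to hand to the next trial. The effect estimate may carry a phase difference in earlier gain. The SD may include variation that a simple adjustment would remove.

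**Working it through.** The plan gives no SD, correlation, effect size or sample size for this outcome, so there is no figure of its own to reproduce. Timing comes from section 6; every weight figure below is an assumption.

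Notation: *a* = SD of gain before the OGTT, *b* = SD of gain after it, *r* = their correlation, *D* = phase difference in mean gain before the OGTT.

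**1. Time elapsed at allocation.** 24/40 = 60% and 28/40 = 70%, leaving 12–16 weeks. For delivery at 37 weeks: 24/37 = 65% and 28/37 = 76%, leaving 9–13 weeks. These are shares of time, not of weight gained.

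**2. What a phase difference does.** If later gain depends on earlier gain with slope *r·b/a*:

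- contrast in total gain = true effect + *D*(1 + *r·b/a*)
- contrast in gain after the OGTT, unadjusted = true effect + *D·r·b/a*
- either outcome, adjusted for gain before the OGTT = true effect

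With a true effect of −1.5 kg, *D* = +0.5 kg and *a* = *b* = 3 kg:

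| *r* | Total gain | Gain after OGTT, unadjusted | Either, adjusted |
|---|---|---|---|
| −0.3 | −1.15 | −1.65 | −1.50 |
| 0 | −1.00 | −1.50 | −1.50 |
| +0.3 | −0.85 | −1.35 | −1.50 |

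A simulation of 400,000 women per setting gave −1.16, −0.99 and −0.85 for total gain; −1.65, −1.50 and −1.35 for gain after the OGTT; and about −1.5 for either outcome once adjusted. With *D* = 0, all four analyses gave about −1.5.

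**3. Precision.**

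- SD of total gain = √(*a*² + *b*² + 2*rab*)
- SD after adjustment for earlier gain = *b*√(1 − *r*²)

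Central case, *a* = 4, *b* = 2.5, *r* = 0: √(16 + 6.25) = 4.72 kg against 2.50 kg, ratio 0.53. Over *a* = 3–5, *b* = 2–3 and *r* = 0–0.3:

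- smallest ratio (*a* = 5, *b* = 2, *r* = 0.3): 1.91/5.92 = 0.32
- largest ratio (*a* = 3, *b* = 3, *r* = 0): 3.00/4.24 = 0.71

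The direction does not depend on those assumptions. The variance of total gain minus the adjusted variance is *a*² + 2*rab* + *r*²*b*² = (*a* + *rb*)², which is never negative. Adjustment therefore loses no precision beyond one degree of freedom and the cost of any imbalance in the covariate. Unadjusted gain after the OGTT has no such guarantee: with *a/b* = 0.5 and *r* = −0.5, total gain has 0.75 times its variance.

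**4. Choice of outcome under adjustment.** Total gain equals earlier gain plus later gain. With earlier gain in the model, moving it to or from the outcome changes only its own coefficient, by exactly 1. The arm estimate and its standard error are the same.

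**5. Illustration for a later trial.** Two-sided 0.05, power 80%, effect 1.5 kg, *a* = *b* = 3 kg, *n* per arm = 2(1.960 + 0.842)² × SD²/1.5²:

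- gain after the OGTT: 15.70 × 9/2.25 = 62.8, so 63
- total gain, *r* = −0.3: 15.70 × 12.6/2.25 = 87.9, so 88
- total gain, *r* = 0: 15.70 × 18/2.25 = 125.6, so 126
- total gain, *r* = +0.3: 15.70 × 23.4/2.25 = 163.3, so 164

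**The case against.** **Total gain is never stated.** Correct. A reader might infer from section 9.3 that the contrast is in total gain, but linear regression does not settle what the outcome is, and section 8 refers to a protocol not supplied here. What the documents do show is that the outcome is undefined in them. The rest depends on the usual meaning of the term.

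**Bias is not shown.** A reader might infer that the estimate is biased. It is biased through this route only if the two phases differ in earlier gain, and the documents offer no evidence either way.

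**The precision figures rest on assumptions.** They do, and the range uses only non-negative correlations. A negative one is possible: every woman with GDM is referred for diet and activity counselling (section 7), which might slow later gain most in those who had gained most. That can make total gain more precise than unadjusted gain after the OGTT, but not more precise than the adjusted analysis, apart from the small costs in step 3.

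**The plan already covers it.** Section 9.4 checks baseline imbalance, leaves the covariate list open and disclaims causal inference; section 9.1 calls the analyses mainly descriptive and exploratory. This lowers the stakes, and it means the documents do not support saying that a phase difference would be presented as a proven effect. It does not commit anyone to adjust for earlier gain, and estimation is the declared purpose.

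**The SD of total gain is right for some trials.** True for a later trial that analyses total gain unadjusted. It is too large only for one that analyses gain after the OGTT or adjusts for earlier gain.

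**Conclusion.** The point holds as a modest improvement to one exploratory secondary outcome. The documents establish that the outcome's start and end weights are not given, that allocation follows 60–70% of a 40-week pregnancy, that the arms are sequential and non-randomised, and that adjustment for weight or gain at diagnosis is not promised.

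If the outcome is total gain, a phase difference in earlier gain enters the contrast, one-for-one at zero correlation and by more or less otherwise. With no such difference, earlier gain usually adds variance. The 0.32–0.71 ratio of interval widths rests wholly on the assumed SDs and correlation; that adjustment does not widen the interval, beyond the small costs noted, does not.

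A reader might also conclude that switching to gain from the OGTT is enough. It is not: when earlier and later gain are correlated, part of a phase difference remains (−1.35 or −1.65 kg against a true −1.50 kg in the example). Adjustment is what removes it.

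**What to change.** For the arm comparison of gestational weight gain, amend sections 8 and 9.3–9.4 as follows:

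- State the start weight, the end weight and the source of each.
- Always adjust for gain up to the OGTT (or for early or pre-pregnancy weight together with OGTT-visit weight) and for gestational age at diagnosis, whatever imbalance is observed. Total gain and gain after the OGTT then give the same arm estimate.
- Report the residual SD of this model for planning the next trial. Keep unadjusted total gain as a descriptive figure.
- Do not divide by, or adjust for, weeks from OGTT to last weight in the main analysis. That interval arises after allocation and largely reflects gestational age at delivery, itself a listed outcome. Show it only as a sensitivity analysis.

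**Cost.** SAP wording and one antenatal weight abstracted per woman with GDM. For the control phase this may have to be retrospective. The documents do not show that both facilities record a weight at the OGTT visit, so the nearest weight may have to serve. Some weights may be missing, perhaps unequally between phases, and section 9.5 plans no imputation; the number missing should be reported by arm.
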